PRESERVING LUNG VOLUME AT EXTUBATION. A MULTICENTER  
PROSPECTIVE, RANDOMIZED CONTROLLED CLINICAL TRIAL (RCT)

Version 2. August 26th 2022.

SUMMARY:

Introduction: At present, the best spontaneous breathing test (SBT) during weaning from mechanical ventilation is a 30-min test with pressure support 8 cmH2O without PEEP. There is a debate about the possible collapse of some alveolar units during such SBT and during extubation with continuous suctioning. A few experiences show extubation without suctioning as feasible and safe.

Hypothesis: Techniques aimed at preserving lung volume during SBT and extubation can yield higher rates of successful extubation.

Primary objective: To define the rates of successful extubation in two extubation approaches aiming at different levels of lung volume preservation: standard SBT (30-min PSV8 without PEEP followed by extubation with continuous suctioning) versus experimental SBT (PSV8+ PEEP5 followed by extubation without suctioning).

Secondary objectives: Reintubation rate, ICU and hospital stays, and mortality in each group.

Design: Prospective, multicenter, randomized study. Two opposing extubation strategies are compared in randomly assigned patients.

## INTRODUCTION

Weaning refers to the entire process of liberating the patient from mechanical ventilation (MV) and removing the endotracheal tube (ETT).

In the last 20 years, different strategies and ventilatory modalities of weaning have been described (1-4). According to the literature, pressure support ventilation (PSV) and T-tube are the most used strategies in weaning (5-7). Protocols are recommended since their use has been shown to increase extubation success.

The final phase of weaning is known as a spontaneous breathing test (SBT). According to current scientific evidence, there seems to be no difference in the success of extubation and need for reintubation between T-tube and low PSV for two hours (3). Additionally, success rates of extubation are similar for SBTs done with T-tubes for 30 minutes vs. for 2 hours (2), and between those done with low PSV for 30 minutes vs. for 2 hours (4).

Recently, our group demonstrate that a less demanding SBT (low PSV for 30-min) was better tolerated and allow higher rate of extubation success than a more demanding SBT (T-tube for 2-h) (8).

Simultaneously, including a 1-h rest period with MV after SBT and before extubation was able to improve extubation success in another RCT (9). The authors claimed for respiratory muscle rest as the main factor for such unsupported successful breathing, but recruitment of lung volume after SBT may also occur.

There is a debate about the possible collapse of some alveolar units during such SBT and during extubation with continuous suctioning. A few experiences show extubation without suctioning as feasible and safe (10).

Moreover, patients who fail extubation frequently develop hypoxemia that suggests variable degrees of lung collapse. Then, techniques aimed at preserving lung volume in the peri-extubation period may offer additional advantages.

## HYPOTHESIS

Techniques aimed at preserving lung volume during SBT and extubation can yield higher rates of successful extubation.

## OBJECTIVES:

Primary: To determine the rate of successful extubation in two opposite weaning strategies.

Secondary: To determine the ICU stay, hospital stay, hospital survival, and 90-day survival in the two groups. To identify the causes of extubation failure.

## METHODS

Study design and protocol (informed consent in Appendix 1):

Prospective multicenter, controlled, randomized study.

Inclusion criteria: Patients > 18 years who meet weaning criteria (see below) after at least 24 hours of MV, and with informed consent signed by them or their next of kind.

Exclusion criteria: tracheostomy, do-not-reintubate orders, decision of the responsible physician (e.g., due to a preference for a particular weaning technique according to the underlying pathology), absence of informed consent, mental incapacity without legal representation.

Weaning criteria:

- Suitable cough (Ability to raise secretions to the endotracheal tube) (or  $PiMax > -15$  cmH2O).
- Absence of excessive secretions (<3 aspirations in the last 8 hours).
- Resolution or improvement of the pathology that led to intubation.
- Clinical stability (HR <140 bpm, SBP 90-160, without vasopressors or at minimum doses).
- Adequate oxygenation (SatO2 > 90% with FiO2 <0.4).
- Adequate ventilatory mechanics (RR <35 rpm, MIP <-20 cmH2O, Vt > 5 ml / kg, VC > 10 ml/ kg, RR / VT <100 rpm/l).
- Confident awareness level (Glasgow Coma Scale > 13).

Prior to the SBT, attending physicians will state whether they intend to apply prophylactic post-extubation high flow nasal cannula or non-invasive mechanical ventilation. Patients will be in Fowler position (seated at 45° angle), the tracheal secretions will be suctioned before SBT, and FiO2 will remain at the same level than when receiving MV. A cuff-leak test will be performed by deflating the cuff and looking at the difference between inspired and expired volumes.

Patients will be randomized to two weaning strategies (see statistical analysis for more information):

- Standard: PSV 8 cmH2O, PEEP 0 cmH2O for 30 minutes and, when successful, followed by extubation with continuous suctioning.
- Lung volume preservation: PSV 8 cmH2O, PEEP 5 cmH2O for 30 minutes and, when successful, followed by direct extubation without suctioning.

Other components of standard treatment of patients (physiotherapy, nutrition, hydration...) will remain at the discretion of attending physicians and local protocols. During the SBT, if the patient meets any of the criteria for failure (see below), MV will be reconnected with the same parameters as prior to the SBT.

Failure of SBT will be defined as:

- Subjective indexes:

- Neurological causes: Agitation or anxiety. Low level of consciousness (Glasgow Coma Scale <13).
- Increased respiratory work: use of accessory muscles, facial expression suggesting stress, severe dyspnea.

- Objective indexes:

- Hypoxemia: PaO2 <60 mmHg or SatO2 <90% with FiO2 ≥0.5
- Tachypnea: RR > 35 rpm
- Hemodynamic instability: HR > 140 bpm or >20% from baseline; SBP >180 mmHg or >20% from baseline; SBT <90 mmHg; Cardiac arrhythmias.

Patients who fail the SBT will not be randomized in later SBT tests. The day and time of extubation will be recorded in the CRF.

If the patient successfully passes the SBT, an arterial blood gas analysis may be performed at the end of the test.

It is recommended, but not mandatory, to reconnect the patient to MV to rest for 1 hour and, then, proceed to extubation with or without suctioning as randomized.

Extubation failure at 72 hours (regardless of whether reintubation is required) is defined as:

- Respiratory acidosis, pH <7.32, PaCO2 > 45 mmHg.
- SatO2 <90% or PaO2 <60 mmHg with FiO2 ≥50%.
- Tachypnea > 35 rpm.

- Deterioration of the level of consciousness, Glasgow Coma Scale <13.
- Uncontrollable agitation.
- Clinical signs of muscle fatigue.

In extubation failure patients, the attending physician will decide on the treatment, either support with non-invasive ventilation or with high flow nasal cannula, or reintubation as Standard of Care at the discretion of the attending physician..

Patients who present extubation failure will not be randomized in later SBTs.

During the SBT, interventions that the physician considers necessary to monitor the success of the test, such as echocardiography or thoracic ultrasound, may be performed. In the event that the physician considers that the findings of these tests do not guarantee successful extubation despite fulfillment of extubation criteria according to the study protocol, the attending physician's decision will prevail over the study protocol. In these cases, it will be recorded in the CRF as extubation failure due to "other causes of weaning failure".

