***Variables (CRF in Appendix 2):***

Demographic variables: Age, sex, weight, height. Comorbidities: heart disease, neurological disease, COPD, diabetes, cancer, chronic renal insufficiency, liver disease. Variables at admission and during SBT: Diagnosis at admission to the ICU, reason for intubation, APACHE II on admission and on the day of extubation, hospital admission date, and date of admission to the ICU.

At the beginning and at the end of the SBT: FiO2, respiratory rate, SaO2, tidal volume during the SBT. If blood gas analysis is performed prior to extubation: PaO2, PaCO2, pH, bicarbonate and base excess.

Outcome variables: Respiratory failure at 72 hours post-extubation and criteria. If blood gas analysis is performed after failure: PaO2, PaCO2, pH, bicarbonate and base excess.

In cases with respiratory failure and rescue NIV, maximum FiO2, IPAP, and maximum EPAP, as well as the hours of application, will be recorded.

If post-extubation high-flow nasal cannula is used, maximum FiO2 and flow will be recorded.

If the patient is reintubated within 72 hours, the time and cause of reintubation will be recorded.

The CRF will be recorded in the RedCap® platform.

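### Read literally, the SBT saturation failure criterion (FiO2 of 0.5 or more) cannot be triggered in a test held below FiO2 0.4, and no rule says how FiO2 may be raised

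*Combined protocol and SAP*

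**What the plan says.** All references are to the main trial protocol unless the ultrasound substudy is named.

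- **Entry** (Methods, Weaning criteria): "Adequate oxygenation (SatO 2 > 90% with FiO 2 <0.4". The substudy repeats this in its Table 1. Meeting the weaning criteria is a condition of inclusion.
- **FiO2 for the test** (Methods, paragraph on preparation for the SBT): "FiO 2 will remain at the same level than when receiving MV".
- **Failure** (Methods, Failure of SBT, objective indexes): "Hypoxemia: PaO 2 <60 mmHg or SatO 2 <90% with FiO 2 ≥0.5".
- **Action on failure** (Methods): "if the patient meets any of the criteria for failure (see below), MV will be reconnected".
- **Blood gas** (Methods, after a passed SBT): "an arterial blood gas analysis may be performed at the end of the test". The substudy CRF lists gases at the beginning and end of the SBT, also only where they are done.
- **Physician override** (Methods): after monitoring such as echocardiography or thoracic ultrasound, the physician's decision prevails if "the findings of these tests do not guarantee successful extubation despite fulfillment of extubation criteria according to the study protocol". In that case "it will be recorded in the CRF as extubation failure due to" a residual category of weaning failure.
- **Data collected** (Variables): "At the beginning and at the end of the SBT: FiO 2 , respiratory rate, SaO 2", along with tidal volume.

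**The concern.** A failure criterion should be reachable under the conditions of the test it governs. Here the saturation limb refers to an FiO2 that a patient managed as written does not receive. Take a patient at SatO2 89% on FiO2 0.35 (an assumed example). That patient could not have started the SBT, yet does not meet the saturation criterion for failing it.

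This matters more here than it would in many weaning trials. The arms differ in PEEP during the test (0 versus 5 cmH2O), and the rationale is alveolar collapse. The Introduction links extubation failure to hypoxemia that suggests collapse. The limb that does not work is therefore the objective criterion closest to the proposed mechanism.

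Without a working rule, the same desaturation could be handled as an SBT pass, as a stop outside the listed criteria, or as an override. An override is labelled as extubation failure, whereas the planned results keep a separate group for patients who failed the SBT. The person choosing knows the PEEP setting. That is also true of the subjective criteria, but this one is listed as objective.

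**Working it through.** The check is mainly logical. It asks whether the FiO2 values allowed during the test overlap those the failure limb requires.

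**1. Range check.** Allowed: from room air (0.21) to below 0.40, from the entry criterion plus the rule that FiO2 stays at its ventilator level. Required by the saturation limb: 0.50 or more. Overlap: none.

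**2. Distance between the ranges.** The rise needed to reach 0.50 is:
- from the 0.40 ceiling (itself not allowed): 0.50 − 0.40 = 0.10, and 0.50/0.40 − 1 = 25%;
- from an assumed 0.35: 0.15, and 0.50/0.35 − 1 = 43%;
- from an assumed 0.30: 0.20, and 0.50/0.30 − 1 = 67%.

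So any permitted entry level needs a rise of more than 0.10. These figures describe the gap between two rules. They do not measure patients, bias or risk.

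**3. Scope of the FiO2 qualifier.** The sentence can be read two ways.

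| Qualifier covers | Saturation limb | PaO2 limb |
|---|---|---|
| both measures | unreachable | unreachable |
| saturation only | unreachable | works at any FiO2, but only if an optional gas is drawn |

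The saturation limb fails on both readings.

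**4. Comparison with the other limits.** Respiratory rate must be below 35 to enter and above 35 to fail. Heart rate must be below 140 to enter and above 140 to fail. The upper systolic limit moves from 160 to 180 mmHg, but a patient can reach 180 during the test. Oxygenation is the only one of these whose failure limit depends on a setting that the test, read literally, does not allow. The 72-hour extubation failure definition uses the same 50% FiO2 level, and it works there because FiO2 is not fixed after extubation.

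**5. What still catches a desaturating patient.** Tachypnea, increased work of breathing, agitation, a heart rate or systolic pressure more than 20% from baseline, arrhythmia, and possibly PaO2. What remains is isolated desaturation.

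**6. Sample size.** The plan's figure reproduces and does not depend on this point. With 82% versus 87%, two-sided alpha 0.05, 80% power and pooled variance under the null: n = [1.960 × √(2 × 0.845 × 0.155) + 0.842 × √(0.82 × 0.18 + 0.87 × 0.13)]² / 0.05², which rounds up to 822 per group.

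**The case against.** The best counter-argument is that the FiO2 sentence belongs to a list of preparations (position, suctioning, FiO2) and may only mean that FiO2 is not changed on moving to the SBT. Recording FiO2 at both ends of the test fits that reading, and the failure limb itself presupposes that 0.5 can be reached. The intended sequence may be to start at the ventilator FiO2, raise it for desaturation, and call failure if saturation stays low at 0.5.

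That reading is possible, so "cannot" holds only for the literal text. However, the verb used favours a held FiO2, and recording a value does not authorise changing it. Even on the softer reading, no text says when, how far or for how long to raise FiO2, which leaves the criterion to local practice in the 34 centres named in the substudy.

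Three further objections carry weight:
- The physician may obtain a blood gas during the test, and the tests named in the override are examples, not a closed list. Some cases will be caught this way. It is less clear that an oximeter reading alone counts as such a finding.
- The rule is the same in both arms, and patients who are extubated are still assessed at 72 hours against a definition that works. This limits the consequence but does not settle how the SBT itself is classified.
- Simply deleting the FiO2 qualifier would make even a brief dip at low FiO2 a failure, and patients who fail are not randomised again in later SBTs. The fix therefore needs a persistence condition.

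**Conclusion.** The point stands in limited form and should be corrected. On the literal text the saturation limb cannot fire. On the softer reading it lacks the step that would let it fire. Either way the protocol has no usable saturation threshold for stopping the SBT. The gap covers isolated desaturation not caught by another criterion or by a discretionary gas.

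A reader might infer more, and the documents do not support it:
- *That desaturating patients must be left on the test or extubated.* A listed criterion is sufficient for reconnection. Nothing makes it the only ground for stopping.
- *That hypoxemia can never fail the SBT.* PaO2 below 60 mmHg may still count, depending on how the qualifier is read.
- *That the primary comparison is biased or underpowered.* The number of isolated desaturations, their split by arm and their handling are all unknown. Any figure would come from an assumed frequency.
- *That the 72-hour endpoint shares the fault.* It does not.

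The conclusion assumes that patients enter on FiO2 below 0.4 as required, and that no text outside the documents reviewed allows FiO2 to be raised during the test.

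**What to change.** Amend the SBT hypoxemia criterion in one of two ways:

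1. Failure is sustained SatO2 below 90%, with the duration stated, or PaO2 below 60 mmHg if a gas is drawn, at the FiO2 held during the SBT; or
2. FiO2 may be raised to 0.5 during the SBT, and failure is SatO2 remaining below 90% at that level.

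With either option, apply the same rule in both arms, state whether any FiO2 qualifier governs PaO2, and record these stops as SBT failures, separate from the override category.

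The cost is a short amendment. The start and end values of FiO2 and SaO2 are already in the CRF. There are two downsides. Some additional SBT failures may occur, and if the trial's rationale is right, more of them may fall in the PEEP 0 arm. An amendment after recruitment starts (planned for October 2022 to May 2024) would also put two failure rules in one trial. In that case, tabulate by arm the patients with end-of-SBT SaO2 below 90%, with their FiO2 and pass/fail call, and include any placed in the override category.

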***Variables (CRF in Appendix 2):***

Demographic variables: Age, sex, weight, height. Comorbidities: heart disease, neurological disease, COPD, diabetes, cancer, chronic renal insufficiency, liver disease. Variables at admission and during SBT: Diagnosis at admission to the ICU, reason for intubation, APACHE II on admission and on the day of extubation, hospital admission date, and date of admission to the ICU.

At the beginning and at the end of the SBT: FiO2, respiratory rate, SaO2, tidal volume during the SBT. If blood gas analysis is performed prior to extubation: PaO2, PaCO2, pH, bicarbonate and base excess.

Outcome variables: Respiratory failure at 72 hours post-extubation and criteria. If blood gas analysis is performed after failure: PaO2, PaCO2, pH, bicarbonate and base excess.

In cases with respiratory failure and rescue NIV, maximum FiO2, IPAP, and maximum EPAP, as well as the hours of application, will be recorded.

If post-extubation high-flow nasal cannula is used, maximum FiO2 and flow will be recorded.

If the patient is reintubated within 72 hours, the time and cause of reintubation will be recorded.

The CRF will be recorded in the RedCap® platform.

## RISKS AND BENEFITS OF THE STUDY

We consider that randomizing patients to one or another strategy should not pose any additional risk.

Likewise, the patients participating in the study will not obtain a direct benefit. However, if we determine that one of the weaning strategies results in a higher rate of successful extubation, we could adapt this strategy in our daily clinical practice for benefit of future patients.

Given the characteristics and the absence of clinical risk, the need for additional insurance has not been considered.

## STATISTICAL ANALYSIS AND CALCULATION OF SAMPLE SIZE

Considering a basal extubation success of 82%, estimating an increase in absolute extubation success rate of 5%, with an alpha error of 0.05 and a power of 80%, requires a sample size of 822 patients in each group. With the participating hospitals, this sample will be obtained in 12 to 18 months, according to the recruitment rates. Recruitment will begin in October 2022 and will end in May 2024.

The randomization will be carried out with the built -in tool of the REDCAP® platform with computerized random numbers tables and patient N blocks for each hospital (researchers will be blinded on this data). Each participating center will have two different Redcap® profiles. The "recruiter" will have access only to the randomization tool and will not have access to data entry (only one recruiter per center). Another profile will be the "researcher" that will have access to randomization and data entry (as many profiles as researchers for each center). Researchers will have access to the data of their centers, but cannot access the data of other centers. Only trial coordinators will have access to data from all centers.

Before analyzing the results and managing the database, we will check the database to detect errors such as variables or repeated patients, or the lack of values in the

variables through the statistical computer program SPSS version 22® and R-Studio version 3.0®.

When half of the sample has been recruited, a preliminary analysis will be conducted to identify the trend of the results in the primary outcome. If significant ( $p < 0.005$ ) results have been obtained in one of the two randomization groups at that point, the inclusion of patients will be stopped. This analysis will be blinded to investigators.

In the descriptive analysis, quantitative variables will be expressed as means and standard deviations (if normally distributed) and as medians and interquartile ranges (if non-normally distributed). Qualitative variables will be expressed as frequencies and percentages.

Quantitative variables will be compared by Student's t-tests and qualitative variables by chi-square or Fisher's test.

Survival analyses for respiratory failure at 72 hours, reintubation at 72 hours, and mortality at 3 months will be performed with Kaplan-Meier curves with logarithmic rank test for comparison between both groups.

To identify causes of extubation failure, multivariate by logistic regression will be performed, adjusting for confusion factors such as type of pathology, blood gas analysis variables, and center.

The results will be analyzed in three ways:

1. Patients who failed the SBT.
2. Patients who passed the SBT:
  - a. Successful extubation
  - b. Reintubation within 72 hours.

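### An efficacy stop at p<0.005 at half the sample, with no lower level set for the final test, gives an overall type I error of about 0.052 instead of 0.05

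*Combined protocol and SAP*

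**What the plan says.** All of the relevant text is in the combined protocol and SAP, under the main trial's heading Statistical analysis and calculation of sample size.

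- **Sample size.** The assumptions are a control success rate of 82% and an absolute gain of 5 points, "with an alpha error of 0.05 and a power of 80%, requires a sample size of 822 patients in each group". Sidedness is not stated.
- **Interim look.** "When half of the sample has been recruited, a preliminary analysis will be conducted", on the primary outcome.
- **Stopping rule.** "If significant ( $p < 0.005$ ) results have been obtained" "in one of the two randomization groups at that point", inclusion stops.
- **Test.** Categorical variables are compared by chi-square or Fisher's test. No significance level is attached to that sentence.

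The only alpha given for the main trial is the 0.05 in the sample-size sentence. Neither this section nor any other sets a final critical level, a spending function or a named group-sequential boundary. The ultrasound substudy has its own sample size and does not address the point.

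**The concern.** The stopping rule ends recruitment on a significant primary result, so the interim look is a real opportunity to reject the null hypothesis. Spending 0.005 there and then testing at the full 0.05 gives two chances of a false positive, and their union must exceed 0.05. The plan states 0.05 and makes no provision for the first look.

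What is at stake is the status of a borderline result. A final p just under 0.05 would be called significant on the plan's only stated alpha, although the two-look procedure would then run above 5%. Setting the level after the data are seen would look data-driven. The rule is also not a remote contingency: under the planned effect, the chance of crossing at the interim is about one in five.

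**Working it through.** **Inputs** (all from the main trial's statistical section): success 0.82 against 0.87; alpha 0.05; power 0.80; 822 per group; one look at half the sample (411 per group); interim threshold p<0.005. Two-sided testing is inferred from step 1 and from a stopping rule that can favour either group. The final level of 0.05 is also inferred, because no other level is given.

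**1. Reproduce the plan's sample size.** With pooled variance, no continuity correction and mean rate 0.845:

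n = [1.960 × √(2 × 0.845 × 0.155) + 0.842 × √(0.82 × 0.18 + 0.87 × 0.13)]² / 0.05²

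= (1.0031 + 0.4297)² / 0.0025 = 2.0531 / 0.0025 = 821.2, rounded up to **822**.

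This matches exactly, with power 80.04%. The alternatives do not match:

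| Variant | n per group |
|---|---|
| Two-sided, continuity correction | 861 |
| One-sided | 647 |
| One-sided, continuity correction | 687 |
| Unpooled variance | 818–819 |
| Arcsine | 817–818 |

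The sample size is therefore that of a single two-sided test at the full 0.05.

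**2. Overall type I error as written.** Under the null, the interim and final statistics Z1 and Z2 are bivariate normal with correlation √0.5 = 0.707. The critical values are 2.807 (p = 0.005) and 1.960 (p = 0.05).

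Overall alpha = 1 − P(|Z1| < 2.807 and |Z2| < 1.960) = **0.0519**.

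The excess is 0.0519 − 0.05 = 0.0019. The simple sum, 0.055, is only an upper bound, because most trials that cross at the interim would also be significant at the end.

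**3. Sensitivity.**
- Timing: overall alpha is 0.0525 if the look falls at 40% of the information and 0.0513 at 60%.
- Binomial simulation of the chi-square test (411 then 822 per group, 4 million trials at each null rate): about 0.052 at success rates of 82%, 84.5% and 87%.
- Fisher's exact test at both looks: about 0.043 to 0.045.

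**4. Final level that restores 0.05.** Holding the interim at p<0.005 and solving 1 − P(|Z1| < 2.807 and |Z2| < c) = 0.05 gives c = 1.977, a nominal final level of **0.0481**. Rounding down to 0.048 gives an overall alpha of 0.0499.

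**5. Power at 822 per group, 82% against 87%, over both looks.** The drift is matched to the fixed-design power of 80.04%, that is 1.960 + 0.843 = 2.803.

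| Final level | Overall alpha | Power |
|---|---|---|
| 0.05 (as written) | 0.0519 | 80.2% |
| 0.0481 | 0.0500 | 79.7% (0.7975) |

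Using the unpooled variance for the drift gives 80.3% and 79.9%; the difference between the two levels is about 0.5 points either way. The probability of crossing at the interim is P(Z > 2.807 − 2.803 × 0.707) = P(Z > 0.825), about **20%**. Restoring 80% power for the final test alone at the lower level takes 832 per group.

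**The case against.** The strongest reply is that the plan never says the final test is at 0.05. That figure appears only as a sample-size input. If it is meant as the overall error, a final level near 0.048 would be consistent with the text and merely unwritten, and the match of 822 to a single-look formula shows only that the sample size was not adjusted. This is correct as far as it goes, and the 0.0519 is conditional on it. It does not rescue the plan: if 0.05 is used, alpha is exceeded, and if a lower level was intended, it is not written down. Reading the only stated alpha as the level of the final test is the natural reading.

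Second, the direction depends on the test. Fisher's exact test at both looks would keep the actual error below 0.05. The plan allows chi-square or Fisher without committing to either, and 822 matches the uncorrected chi-square, so the design cannot rely on Fisher's conservatism.

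Third, the excess is tiny: about 2 extra false positives per 1,000 null trials, relevant only for a final p in a window 0.0019 wide. The strict interim threshold already removes most of the inflation, and 822 per group remains adequate in practice. All of that stands and limits the weight of the point. It does not make the stated alpha correct.

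**Conclusion.** The concern holds. As written, the plan pairs an efficacy stop at p<0.005 with an unadjusted final alpha of 0.05, for an overall two-sided type I error of 0.0519. This rests on three assumptions: the final test is at 0.05, the test is a two-sided chi-square, and the look falls at about half the information. The direction does not change for looks at 40% to 60%. It would reverse only if Fisher's exact test were used at both looks, which the plan does not specify.

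The sample-size arithmetic is right for a single test; the missing piece is the allowance for the interim look. The size is small, so this should be corrected but does not threaten the trial's interpretability.

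**What to change.** In the main trial's statistical section, before any comparative results are seen:

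1. Keep the interim threshold at p<0.005, and describe it as a two-sided comparison of the primary outcome between the groups. The phrase "in one of the two randomization groups at that point" does not describe such a test.
2. State that the final primary test is two-sided at p<0.048, reported with a 95.2% confidence interval (100 − 4.8), and that overall alpha is 0.05.
3. Name the test used at both looks. If it is the chi-square, the levels above apply directly.

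The cost is one or two sentences and about 0.5 points of power at 822 per group, with no extra patients. If the sponsor prefers to keep 80% power for the final test alone, 832 per group does so: 10 more per group, 20 in total.
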